6.5.3.2 Dose Modification for Patients with Stable Disease

For patients with SD, regardless of indication, after completion of one year of treatment from Cycle 1, Day 1, they will undergo a tumor assessment and discontinue treatment. Patients will remain on study, and upon disease progression, may be rechallenged with treatment at a dose of 520 mg/m² BID (for non-ATRT patients) or at a dose of 1200 mg/m² BID (for ATRT or any INI1-negative tumors with CNS involvement), based on the treating Investigator’s decision. Overall treatment should not exceed 2 years of cumulative dosing (Figure 4).

Figure 4 Dose Modification Schematic for Patients With Stable Disease

Abbreviations: ATRT= atypical teratoid rhabdoid tumor, BID= twice daily, C1D1= Cycle 1, Day 1, CNS= central nervous system, CR= complete response, INI1= integrase interactor 1, PD = progressive disease, PR= partial response, SD= stable disease.

6.6 Treatment Discontinuation

If a new case of **CCI**/T-ALL or MDS occurs, regardless of dose or time on treatment, then the patient will be discontinued from treatment, followed up for resolution, then discontinued from the study (see Section 3.4).

All patients are to discontinue participation on the study after 2 years of cumulative treatment, regardless of whether they came off study due to clinical response or if they reduced dose. For example, if a decision is made by the treating Investigator to pause treatment after 1 year of response, the 2 years of maximum treatment would only be accounted for during the time the patient is receiving therapy. Alternatively, if the decision is made by the treating Investigator to reduce dose, the maximum of 2 years would still apply, regardless of the dose of drug received.

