3.5 Estimated Study Duration

3.5.1 Study Duration for Participants

The study duration is approximately 24 months for each subject. The duration of screening for each subject will be approximately 14 days. The subject accrual period is planned for approximately 15 months. The duration of treatment will vary for each subject. Subjects may receive tazemetostat for a cumulative maximum of 2 years. Subjects will be followed for safety for approximately 30 days after the last dose of tazemetostat. For subjects that discontinue dosing, participation will continue for survival follow-up and response for 2 years from first dose of tazemetostat.

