6.5 Dose Modification

During dose escalation, dose modifications are not allowed during Cycle 1. Any AE that is severe enough (at the discretion of the Investigator and with permission of the Sponsor/Medical Monitor) to warrant a dose reduction during Cycle 1 will be discussed with the Medical Monitor prior to resumption of study treatment.

Subjects who have an interruption in treatment for >14 days may restart treatment with tazemetostat after consultation with the Medical Monitor.

For any case of CCI /T-ALL, MDS/AML, or other myeloid malignancies like MPN, tazemetostat will be discontinued and the patient will be followed until resolution of the event.

No dose modification is required for the following Grade 3 or greater non-hematologic toxicities:

- Transient fatigue or asthenia
- Transient myalgia or arthralgia
- Nausea that resolves to <Grade 2 within 7 days (with or without anti-emetics)
- Vomiting that resolves to <Grade 2 within 48 hours (with or without anti-emetics)
- Diarrhea that resolves to <Grade 2 within 48 hours

For subjects in the dose-escalation portion of the study, refer to Table 4 for a description of dose levels to be used for dose modification. For example, a dose reduction of one dose level for a subject on a dose of 1200 mg/m² BID would be 900 mg/m² BID and that for a subject at a dose of 900 mg/m² BID would be 700 mg/m² BID.

For subjects on the dose expansion portion of the study, refer to Section 5.3 for new patient dosing levels.

- For subjects starting at 1200 mg/m² BID, refer to Table 6, below, for a description of dose level modifications.
- For subjects on the tablet formulation (Cohort 4), refer to CCI for instructions on how to administer tablets for each dose level.

Table 6. Dose Modification/Dose Reduction for Dose Expansion Portion

Starting Dose	1200 mg/m ² BID - OR - discontinue
Dose Level - 1	900 mg/m ² BID - OR - discontinue
Dose Level - 2	700 mg/m ² BID - OR - discontinue
Dose Level - 3	520 mg/m ² BID - OR - discontinue

- For subjects starting at the 520 mg/m² BID dose level in the dose expansion portion, no dose modifications are permitted. For these subjects, dosing may be interrupted for up to 14 days to allow resolution of AEs, and subjects must be discontinued if the AE does not resolve with dose interruption.

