6.5.3 Dose Modification due to Risk of Adverse Events of Special Interest

6.5.3.1 Dose Modification After Complete or Partial Response

For all responding patients (with CR or PR), regardless of indication, the dose will be either reduced to 520 mg/m² BID, or stopped at one year from the first observed response based on the treating Investigator’s decision. Patients will remain on study, and upon disease progression, may be rechallenged with treatment at a dose of 520 mg/m² BID for non ATRT patients, or at dose 1200 mg/m² BID for patients with ATRT or any INI1-negative tumors with CNS involvement. Overall treatment should not exceed 2 years of cumulative dosing (Figure 3).

Figure 3 Dose Modification Schematic for Patients With Complete or Partial Response

[figure not shown]

Abbreviations: ATRT= atypical teratoid tumor, CNS= central nervous system, CR= complete response, INI1= Integrase interactor 1, PD= progressive disease.

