- v. **Disease Assessment:** 18 F-DG-PET scan to be performed if clinically indicated at the Investigator’s discretion. It is not a required disease assessment.
- w. **Post-Treatment/Early Termination Visit:** A Post-Treatment/Early Termination visit will be conducted within 30 days (\pm 3 days) after last dose of tazemetostat; prior to the start of a new treatment or therapy; or if the subject's participation is terminated early. This may occur at the time of treatment discontinuation (e.g., at the visit at which the decision to discontinue treatment occurs) or up to 30 days after the final dose of study drug. AE and concomitant medication data must be collected for 30 days after the final dose of study drug, or until the start of new therapy. If subject is unable to return to the clinic for assessment of AEs this may be done by telephone as long as the study subject does not require laboratory and/or other assessments related to any new or ongoing AEs, in which case a clinical visit will be required. In the event of a continuing AE, the subject will be asked to return for follow-up until the AE has resolved or is deemed to be continuing indefinitely.
- x. **Follow-Up for Progression-Free Survival:** Subjects who discontinue study treatment for reasons other than disease progression will continue to have disease assessments, when possible, every 8 weeks until disease progression or death.
- y. **Follow-Up for Overall Survival:** Subjects who permanently discontinue study treatment will be followed (by phone, email, or clinic visit) for survival every 16 weeks until death, withdrawal of consent, or they are lost to follow-up. Survival follow-up will continue for 2 years for each subject or until 80% of subjects enrolled have died. All anticancer therapies will be collected (the Sponsor may choose to stop the collection of therapies after the first anticancer treatment). Additionally, AESI and subsequent anti-cancer therapy information will be collected throughout the survival follow up.

- z. **Annual Assessments:** Annual assessments will be conducted including to review for AEs of special interest, tumor response if PD has not been previously reported, and PK (see footnote “o”).
- aa. **Optional Chest Ultrasound:** An optional chest ultrasound may be performed at the Investigator’s discretion to monitor for early signs of CCI/T-ALL.

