9.4 Survival Follow-Up

Subjects who discontinue study treatment for reasons other than disease progression will continue to have disease assessments, when possible, every 8 weeks until disease progression or death. In addition, subjects who permanently discontinue study treatment will be followed (by phone, email, or clinic visit) for survival every 16 weeks until death, withdrawal of consent, or they are lost to follow-up. AESI and subsequent anti-cancer therapy information will be collected throughout the survival follow up.

Survival follow-up will continue for 2 years for each subject or until 80% of subjects enrolled have died.

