 - Epithelioid malignant peripheral nerve sheath tumor
 - Extraskelatal myxoid chondrosarcoma
 - Myoepithelial carcinoma
 - Renal medullary carcinoma
 - Chordoma (poorly differentiated or de-differentiated)
 - Other INI1-negative malignant tumors with Sponsor approval
- Cohort 4 – approximately 12 subjects with one of the tumor types defined in Cohorts 1 through 3 or synovial sarcoma with SS18-SSX rearrangement

Subjects enrolled in cohorts 1-3 will receive the RP2D of 1200 mg/m² BID of tazemetostat in oral suspension. Subjects enrolled in cohort 4 will initially receive 800 mg/m² TID (2400 mg/m²/day) of tazemetostat administered as tablets, with the possibility to switch to BID tablet dosing or suspension dosing in subsequent cycles if unable to comply with the TID schedule. Cohort 4 was added to evaluate the administration of the tazemetostat tablet formulation in pediatric subjects who can swallow tablets, which may be more palatable.

Escalation and Expansion

Subjects will discontinue study treatment at the time of disease progression, development of an unacceptable toxicity, withdrawal of consent by subject and/or parent, or after 2 years of cumulative dosing or termination of the study.

Subjects also will undergo medical history assessment, physical examinations (PEs); vital sign measurements; echocardiogram (ECHO); performance status (Lansky/Karnofsky) assessments, blood sample collection for hematology, chemistry, PK, and PD markers; electrocardiograms (ECGs); adverse event (AE) assessments; concomitant medication assessments; and pregnancy testing for females of childbearing potential.

The study duration is approximately 24 months for each subject. The duration of screening for each subject will be approximately 14 days. The subject accrual period is planned for approximately 15 months. The duration of treatment will vary for each subject. Subjects may receive tazemetostat for a cumulative maximum of 2 years. Subjects will be followed for safety for approximately 30 days after the last dose of tazemetostat. For subjects that discontinue dosing, participation will continue for survival follow-up and response for 2 years from first dose of tazemetostat.

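### Section 6.6 takes a resolved T-ALL or MDS case off study, which conflicts with the 2-year survival and AESI follow-up set elsewhere in the protocol and SAP

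*Protocol*

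**What the plan says.** Section 6.6 covers a new case of T-ALL (the term paired with it is redacted) or MDS, at any dose and any time on treatment. The patient is to be "discontinued from treatment, followed up for resolution, then discontinued from the study (see Section 3.4").

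The follow-up sections say something else:

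- Table 11 footnote y (Section 8.1): "Subjects who permanently discontinue study treatment will be followed (by phone, email, or clinic visit) for survival every 16 weeks until death". The same sentence adds withdrawal of consent and loss to follow-up as the other individual stopping points.
- Section 9.4 repeats that rule and adds "AESI and subsequent anti-cancer therapy information will be collected throughout the survival follow up". It runs for 2 years for each subject or until 80% of enrolled subjects have died.
- Section 3.5.1: for subjects who stop dosing, "participation will continue for survival follow-up and response for 2 years from first dose of tazemetostat".
- SAP 3.1: "For subjects that discontinue dosing, participation will continue for survival follow-up and response for 2 years from first dose of tazemetostat".

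Two further sections deal with the same kind of event and do not mention study exit. Section 6.5 says that "tazemetostat will be discontinued and the patient will be followed until resolution of the event". Section 3.4.1, which belongs to the section that 6.6 cites, stops the patient's treatment and suspends new enrollment.

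**The concern.** Once the event has resolved inside the follow-up window, a site cannot obey both rules. Section 6.6 ends participation. Section 9.4 schedules the next contact and stops only for death, withdrawn consent, loss to follow-up or the study-wide cap.

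The children concerned have had a second malignancy of the type the protocol singles out for monitoring. If 6.6 is followed, no scheduled contact remains to pick up a relapse, a later myeloid malignancy or a death. SAP 15.3 then censors OS at last contact, so the censoring is triggered by a possibly drug-related event and may be informative.

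**Working it through.** The plan gives no figure on this point to reproduce. The first check compares the rules; the second sizes the consequence.

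**Rules compared**

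| Section | Stops treatment | Follows event | After resolution |
|---|---|---|---|
| 6.6 | yes | to resolution | off study |
| 6.5 | yes | to resolution | silent |
| 3.4.1 | yes | silent | silent |
| 9.4, Table 11 footnote y | already stopped | AESI collected | survival contact every 16 weeks, 2 years or 80% deaths |
| 3.5.1, SAP 3.1 | already stopped | silent | survival and response follow-up, 2 years from first dose |

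No follow-up section exempts an AESI case. The example reasons for study removal in Section 9.2 do not include one, although that list is not exhaustive. AESI collection is stated only in 9.4 and footnote y, so 3.5.1 and SAP 3.1 support the survival half of the conflict only. Until the event resolves, both rules keep the child in follow-up.

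**Contacts lost**

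The documents give no onset or resolution times, so the months below are assumptions. Treatment is taken to stop at onset and study exit to fall at resolution. One month is 30.44/7 weeks, so month 24 is week 104.4. Contact k falls at stop week + 16k and is lost if it comes after exit and by week 104.4.

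| Onset / exit (month) | Stop / exit (week) | Contacts lost (week) | Number |
|---|---|---|---|
| 3 / 4 | 13.0 / 17.4 | 29.0, 45.0, 61.0, 77.0, 93.0 | 5 |
| 6 / 9 | 26.1 / 39.1 | 42.1, 58.1, 74.1, 90.1 | 4 |
| 12 / 18 | 52.2 / 78.3 | 84.2, 100.2 | 2 |
| 6 / 18 | 26.1 / 78.3 | 90.1 | 1 |
| 18 / 21 | 78.3 / 91.3 | 94.3 | 1 |
| any / 24 or later | exit at 104.4 or later | none | 0 |

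Six lost contacts need treatment to stop by week 104.4 − 6 × 16 = 8.4 and the event to resolve before the first contact.

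**Effect on 56-week OS**

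Take a cohort of 20 (the planned size of Cohorts 1 to 3) with no other censoring. Let e children die before the AESI child is censored, and l others die between that point and week 56. The AESI child dies before week 56, but the death is not captured.

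- True survival: (19 − e − l)/20
- Kaplan-Meier estimate with the child censored: (20 − e)/20 × (19 − e − l)/(19 − e)
- Difference: (1/20) × (19 − e − l)/(19 − e), which lies between 0 and 0.05

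Examples: e = 12, l = 0 gives 0.350 against 0.400; e = 12, l = 2 gives 0.250 against 0.286; e = 14, l = 3 gives 0.100 against 0.120; e = 14, l = 5 gives 0 against 0.

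Week 56 is month 12.9. Onset, resolution, exit and the uncaptured death must all fall before then.

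**Frequency**

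Section 1.4.2 reports one pediatric AESI with the event name redacted, and Section 1.6.5 gives 90 children treated. If that case is one covered by 6.6, the rate is 1/90 = 1.1% (exact 95% CI 0.03% to 6.0%). That is 20 × 1/90 = 0.2 expected cases in a cohort of 20, and 120 × 1/90 = 1.3 in the planned 120 (0.03 to 7.2 over the interval).

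**The case against.** **A benign reading is available.** Section 6.6 is headed as a treatment rule, and the section it cites only stops treatment and suspends enrollment. The word study is also used loosely: the next paragraph of 6.6 has patients stopping "regardless of whether they came off study due to clinical response", while Section 6.5.3.1 says of responders who stop drug: "Patients will remain on study, and upon disease progression, may be rechallenged". The sponsor may well have meant the treatment phase. That is plausible, but 6.6 lists stopping treatment as its own first step, so the last step would then repeat it, and no text says this is what is meant.

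**It could be a deliberate exception.** A rule for named events can override a general one, and the synopsis calls 2 years from first dose a maximum, which allows an earlier stop. Against that, 9.4 and SAP 3.1 say follow-up continues for 2 years for each subject, and nothing presents 6.6 as an exception.

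**Other rules limit the loss.** Treatment-related events are followed to outcome even after the subject leaves the study (10.8). Late secondary lymphoma stays reportable (10.9), AESIs are reported within 24 hours (10.11), and death records may be used where permitted (9.2). These stand as partial protection. None schedules a contact after resolution, 10.9 names lymphoma only, and the 9.2 provision is written for withdrawn consent.

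**Sections 10.4.1 and 10.4.2 could not be read.** They cover these very events and may contain a follow-up rule. This stands as a limit on the conclusion. It would not remove the wording of 6.6.

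A reader might also infer that AML and MPN cases are mishandled because 6.6 omits them, or that Section 8.5.10 removes dosed children with abnormal marrow genetics from the study. The documents do not show either. Section 6.5 already stops drug for AML and MPN and follows the event, after which 9.4 applies by default. Exclusion criterion 5 covers abnormal genetics at screening, and 8.5.10 does not say whether its exclusion applies after the first dose.

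**Conclusion.** The final step of Section 6.6 is wrong as written, because its literal meaning conflicts with the follow-up rules in both documents. Severity is minor. It matters only when the event resolves before the 2-year or 80%-deaths cap, and few children are likely to be affected.

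The 1.1% rests on reading the redacted AESI as a case covered by 6.6. The contact counts rest on assumed timings. A reader might take the 5 points as a likely bias in OS. It is the ceiling for a single uncaptured death after early onset, resolution and exit, and with about 0.2 expected cases per cohort the expected shift is far smaller. OS is a secondary endpoint. The primary ORR depends on confirmed tumor responses rather than survival contact, so its decision rule is unaffected. The main loss is late safety information on the children in whom it is most wanted.

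**What to change.** In Section 6.6, replace the last of the three steps, the one that takes the patient off study, with: *and continues survival and AESI follow-up per Section 9.4*. Check that Sections 10.4.1 and 10.4.2 say the same. No change to Section 8.5.10 or to the list of events in 6.6 is needed for this point.

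The cost is one phrase in the next amendment and up to about 6 phone or email contacts per affected child. These are an existing procedure within the existing 2-year window. The downside is longer contact with families whose child has had a second malignancy.

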6.7 Continuation of Treatment

In subjects who do not have evidence of clinical or radiographic disease progression and who do not experience unacceptable toxicity, additional cycles of tazemetostat beyond Cycle 1 may be given at the Investigator's discretion with the subject's or his/her legal representative consent.

Prior to declaring progressive disease, the Investigator should be certain that special circumstances on progression defined by RECIST 1.1 are not met. In these situations of equivocal findings of progression, subjects may continue treatment until the next scheduled disease assessment. If progression is confirmed, the date of the previous assessment will be used as the date of disease progression.

The required hematologic parameters for continuation of treatment for the second and subsequent cycles are the following:

- Platelet count must be $\geq 50 \times 10^9/L$
- ANC $\geq 1.0 \times 10^9/L$, and
- Any Grade 3 or higher toxicity must have resolved to Grade 1 or baseline

Study treatment may be interrupted for up to 14 days. Treatment interruptions longer than 14 days need Medical Monitor approval to proceed.

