- o. **PK:** Blood samples for PK analysis will be collected only at annual assessments. For subjects who are undergoing disease assessment that includes CSF collection for PK (see footnote “p”), draw PK blood sample within 30 minutes of CSF sampling and both samples may be obtained between 0-8 hrs post-dose. A 1 mL blood sample will be collected at the annual time point for subjects \geq 1 year of age. A 0.5 mL blood sample will be collected at the annual time point for subjects < 1 year of age. All PK blood samples may be drawn from central venous catheter or peripheral blood draw and should be \pm 15 min from the scheduled draw time after dosing. The exact time of draw must be recorded. See Section 8.2 for window timing allowances.
- p. **CSF PK:** CSF PK samples will be collected only for subjects who require CSF sampling for disease assessment at Screening after consent is signed and at time of the first disease assessment. If a CSF sample is obtained for tumor assessment, 1 mL of CSF should be collected for CSF PK with paired blood sample for PK collected within 30 minutes of the time that the CSF sample is obtained. Both samples should be obtained between 0-8 hours post-dose
- q. **CCI**
- r. **Bone Monitoring:** Assessment of tibial growth plate, total calcium, phosphorus, magnesium, albumin will be performed during Screening or prior to dosing on Day 1 and then every 6 months while receiving study treatment.
- s. **CCI**
- t. **Tumor Biopsy:** A tumor biopsy will be requested, where medically feasible, at disease progression.
- u. **Disease Assessment:** Tumor assessments by disease-appropriate standard criteria (RECIST 1.1 or RANO) using CT, MRI of known sites of disease as clinically indicated. For subjects with bone disease or CNS disease at baseline, for cycles 1 through 12, a bone or brain scan, respectively, is required every 8 weeks or sooner, if clinically indicated. For cycles 13 and beyond, a bone or brain scan is required every 13 weeks, or sooner, as clinically indicated. Tumor assessments must be performed at Screening and every 8 weeks (\pm 3 days) from start of dosing, irrespective of treatment delays, (during Weeks 8, 16, etc.) or sooner, if clinically indicated. For subjects who stop treatment after one year of first response (CR or PR) or after one year of treatment for subjects with SD, disease assessments should be conducted every 8-12 weeks or according to institutional standards until relapse.

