- In the presence of measurable disease, progression on the basis of solely non-target disease requires substantial worsening such that even in the presence of SD or PR in target disease, the overall tumor burden has increased sufficiently to merit discontinuation of therapy.
- Sites of non-target lesions, which are not assessed at a particular time point based on the assessment schedule, should be excluded from the response determination (e.g., non-target response does not have to be "NE").

New Lesions

New malignancies denoting disease progression must be unequivocal. Lesions identified in follow-up in an anatomical location not scanned at baseline are considered new lesions.

Any equivocal new lesions should continue to be followed. Treatment can continue at the discretion of the Investigator until the next scheduled assessment. If at the next assessment the new lesion is considered to be unequivocal, progression should be documented.

Evaluation of Overall Response

The best overall response is the best response recorded from the start of study treatment until disease progression/recurrence (taking as reference for progressive disease the smallest measurements recorded since the treatment started). The subject's best response assignment will depend on the achievement of both measurement and confirmation criteria.

Best Overall Response for Subjects with Target (+/- Non-Target lesions) Disease

Target Lesions	Non-Target Lesions	New Lesions	Overall Response	Best Overall Response when Confirmation is Required*
CR	CR	No	CR	≥4 weeks Confirmation**
CR	Non-CR/Non-PD	No	PR	≥4 weeks Confirmation**
CR	Not evaluated	No	PR	
PR	Non-CR/Non-PD/not evaluated	No	PR	
SD	Non-CR/Non-PD/not evaluated	No	SD	
PD	Any	Yes or No	PD	no prior SD, PR or CR
Any	PD***	Yes or No	PD	
Any	Any	Yes	PD	

Abbreviations: CR, complete response; PD, progressive disease; PR, partial response; SD, stable disease

* Refer to RECIST 1.1 manuscript for further details on what is evidence of a new lesion.

** Only for non-randomized trials with response as primary endpoint.

*** In exceptional circumstances, unequivocal progression in non-target lesions may be accepted as disease progression.

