15.2. PROGRESSION-FREE SURVIVAL

- PFS per appropriate criteria will be analyzed and listed for the ITT population only for the dose expansion phase of the study. PFS is defined as the interval of time (in weeks) from the date of first dose of study drug and the earliest date of disease progression or death, from any cause. For subjects who progressed or died after an extended period without adequate assessment, PFS will be censored at their date of last adequate assessment prior to progression or death even if subsequent information is available regarding progression or death. An adequate assessment is defined as an assessment where the Investigator determined response is CR, PR, or SD. The date of response at that assessment will be used for censoring.
- For subjects who receive subsequent anticancer therapy prior to the date of documented progression or death, PFS will be censored at the last adequate assessment (i.e., last assessment of CR, PR or SD) prior to the initiation of that anticancer therapy.
- For subjects who do not progress or die, PFS will be censored at the date of the last adequate tumor assessment.

PFS censoring rules are defined in Table 4 below.

In dose expansion, PFS will be summarized by cohort and overall. PFS will be analysed using the Kaplan-Meier method. Median PFS, first and third quartiles and associated 95% 2-sided CIs, will be estimated using the Brookmeyer-Crowley method [Brookmeyer, 1982]. PFS at 24 weeks and 56 weeks along with the associated 2-sided 95% CIs, will be provided. Kaplan-Meier PFS curves also will be provided.

Table 4: Date of Event of Censoring for PFS

Situation	Date of Event (PD/Death) or Censoring	Outcome: Event (PD/Death) or Censored
No (or inadequate) baseline tumor assessments and the subject has not died	Date of Study Day 1	Censored
No post-baseline assessments and the subject has not died (if the subject has died follow the rules for death indicted at the bottom of the table)	Date of Study Day 1	Censored
Progression documented between scheduled visits	Date of assessment of progression ¹	Event
No progression (or death) and no new anti-cancer treatment documented	Date of last ‘adequate’ assessment of response ²	Censored
No progression (or death) and new anti-cancer treatment documented	Date of last ‘adequate’ assessment of response ² on or prior to starting anti-cancer therapy	Censored

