New anti-cancer treatment started (prior to documented disease progression or death). ³	Date of last ‘adequate’ assessment of response ² on or prior to starting anti-cancer therapy	Censored
Death before first PD assessment (or Death at baseline or prior to any adequate assessments)	Date of death	Event
Death between adequate assessment visits	Date of death	Event
Death or progression after one missed visit (with 2 week window)	Date of last ‘adequate’ assessment of response ² prior to missed assessments	Censored

¹ The earliest of (i) Date of radiological assessment showing new lesion (if progression is based on new lesion); or (ii) Date of radiological assessment showing unequivocal progression in non-target lesions, or (iii) Date of last radiological assessment of measured lesions (if progression is based on increase in sum of measured lesions)

² An adequate assessment is defined as a radiological assessment where CR, PR, or SD was determined.

³ If PD and subsequent anti-cancer therapy occur on the same day assume the progression was documented first, e.g., outcome is progression and the date is the date of the assessment of progression). If anti-cancer therapy is started prior to any adequate assessments, censoring date should be the date of Study Day 1.

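### The Protocol backdates a confirmed equivocal progression; the SAP omits that rule and contradicts it for non-target lesions, so PFS and response duration can differ by one assessment interval

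*Protocol*

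**What the plan says.** **Protocol 6.7 (Continuation of Treatment).** After referring to the special circumstances on progression in RECIST 1.1, it says: "In these situations of equivocal findings of progression, subjects may continue treatment until the next scheduled disease assessment". It then fixes the event date: "If progression is confirmed, the date of the previous assessment will be used as the date of disease progression". The previous assessment is the equivocal one.

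**SAP 15.2, Table 4 (PFS).** Progression between scheduled visits is dated to the "Date of assessment of progression". Footnote 1 defines this as the earliest of three dates:

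- (i) New lesion: "Date of radiological assessment showing new lesion (if progression is based on new lesion".
- (ii) Non-target lesions: "Date of radiological assessment showing unequivocal progression in non-target lesions".
- (iii) Measured lesions: the last radiological assessment of those lesions, with nothing on equivocal findings.

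**SAP 15.1, Table 3 (DOR).** The event date is the first assessment that shows progression, or death if earlier. Equivocal scans are not mentioned.

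**SAP 3.2 (Changes to Analyses from Protocol).** It lists changes to laboratory summaries, confidence intervals and subgroups. Progression dating is not among them.

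**Protocol Appendix 4.** For an equivocal new lesion: "If at the next assessment the new lesion is considered to be unequivocal, progression should be documented". This says when to document progression but assigns no date. The FDG-PET rule in the same appendix dates a later-confirmed progression back to the first abnormal scan.

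**The concern.** Two programmers could follow the two documents in good faith and derive different progression dates for the same child. Protocol 14.3.3 requires departures from its analysis plan to be documented in the SAP and the study report, and Protocol 14.4.2 refers to the SAP only for the rules on extended time without assessment, not for dating the event. In a single-arm study with 8-weekly scans and small cohorts, a shift of one scan is large relative to short PFS times. Where the rules differ, the SAP date is always the later one, so the error has a direction: PFS and response duration come out longer.

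**Working it through.** **Inputs**

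- Scan interval on treatment, Protocol Table 11: "Tumor assessments must be performed at Screening and every 8 weeks", with a ±3-day window, placed during Weeks 8, 16 and so on.
- After treatment stops at one year, same table: "disease assessments should be conducted every 8-12 weeks or according to institutional standards until relapse".
- Bone or brain scans from Cycle 13, for subjects with such disease at baseline: every 13 weeks in Table 11, every 12 weeks in Appendix 4.
- Landmarks: 24 and 56 weeks (SAP 15.2), that is 3 × 8 and 7 × 8, so both coincide with scheduled scans.
- Planned size of Cohorts 1 to 3: 20 each (SAP 4.4).
- Duration convention (SAP 7): end date minus start date plus 1, divided by 7. I assume that it applies to PFS.

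**Step 1. The plan's own figures.** Neither document states a design figure for PFS or DOR. The one design calculation is the ORR rule of at least 3 responders in 20. It gives P(X ≥ 3 | n = 20, p = 0.05) = 0.0755 and P(X ≤ 2 | n = 20, p = 0.20) = 0.2061, which match the stated 8% and 21%. These depend only on n, the cut-off and the assumed response rates.

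**Step 2. The rules side by side, for a finding that is equivocal at scan k and confirmed at scan k+1**

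| Basis of progression | Protocol 6.7 | SAP | Same date? |
|---|---|---|---|
| Non-target lesions | scan k | scan k+1, because scan k was not unequivocal | No |
| New lesion | scan k | scan k or k+1; the qualifier is absent and the earliest date is taken | Open |
| Measured lesions | scan k | not addressed | Open |
| DOR, Table 3 | scan k | scan k+1 on the ordinary reading | No, on that reading |

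**Step 3. Size for one subject.** The shift is one interval: 8 weeks on schedule, 8 to 12 weeks or the institutional interval after treatment stops at one year, and 12 or 13 weeks if the deciding scan is a bone or brain scan from Cycle 13. Cycle 13 starts at week 49, so this last case cannot touch the 24-week rate.

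**Step 4. Landmark rates.** A rate changes only if the two dates fall on either side of the landmark.

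- Equivocal on day 165, confirmed 56 days later on day 221: 165/7 = 23.6 weeks and 221/7 = 31.6 weeks. The subject has failed by week 24 under the Protocol and is event-free at week 24 under footnote 1(ii).
- Equivocal on day 169, confirmed on day 225: 169/7 = 24.1 and 225/7 = 32.1. The subject is event-free at week 24 under both rules.

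A scan during Week 24 (days 162 to 168) falls at or before 168/7 = 24.0 weeks; one on day 169 or later does not. With no censoring, each straddling subject moves the rate by 1/20 = 5 points, and an assumed 1 to 4 such subjects by 5 to 20 points.

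**Step 5. Expected effect, under assumptions not in the documents.** Take exponential PFS with a median of 8 to 24 weeks, 8-weekly scans, no censoring, and a fraction f = 10% to 30% of progressions first seen as equivocal and dated one scan late. With S(t) = 2^(−t/median):

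- 24-week rate: rise = f × [S(16) − S(24)]. Median 8, f = 0.1: 0.1 × (0.250 − 0.125) = 1.3 points. Median 16, f = 0.3: 0.3 × (0.5000 − 0.3536) = 4.4 points.
- 56-week rate: rise = f × [S(48) − S(56)]. Median 24, f = 0.3: 0.3 × (0.2500 − 0.1984) = 1.5 points; close to zero for a median of 8.
- Mean PFS: f × 8 = 0.8 to 2.4 weeks.
- DOR: with three responders of assumed duration 16, 24 and 32 weeks, dating the middle one 8 weeks later moves the median from 24 to 32 weeks.

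**The case against.** The strongest reply is that Section 6.7 instructs the investigator how to declare progression, and the SAP analyses investigator assessments. If the site records progression at the earlier scan, much of the SAP would pick up that date, and the SAP's silence would be an omission rather than a change. This has force for new lesions, measured lesions and Table 3. It does not rescue footnote 1(ii), which defines the date by the scan on which non-target progression is unequivocal. Nor does either document say that sites are to re-enter the earlier scan as progression.

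Four stronger readings are tempting, and the documents do not support them:

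- *The SAP contradicts the Protocol for every type of progression.* Only footnote 1(ii) does so expressly. Footnote 1(i) can give the Protocol date.
- *Appendix 4 conflicts with 6.7.* Its new-lesion text assigns no date, and its FDG-PET rule backdates just as 6.7 does.
- *Under the SAP the equivocal scan counts as stable disease.* SAP footnote 2 accepts assessments of CR, PR or SD as adequate, but neither document says how an equivocal scan is recorded. This is a gap to close, not a stated rule.
- *Table 4 footnote 1 also governs DOR.* DOR has its own Table 3 without that footnote, so amending Table 4 alone would leave DOR unchanged.

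It is also fair to say that only descriptive secondary endpoints are involved, that 6.7 cites RECIST 1.1 and does not clearly cover subjects assessed by RANO (including the ATRT cohort), and that the frequency of equivocal progression is not given. All of this limits the size of the point. It does not remove the mismatch.

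**Conclusion.** The point holds in a limited form. The SAP drops the Protocol's backdating rule without declaring it, contradicts it for non-target progression, points the other way for DOR on the ordinary reading of Table 3, and leaves new-lesion and measured-lesion progression open. Where the dates differ, the SAP gives the later one by one assessment interval, normally 8 weeks, and so lengthens PFS and DOR for that subject.

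A reader might infer that every affected subject changes the landmark rates. That does not follow: a rate moves only when the two dates straddle week 24 or 56. The 5 points per straddling subject assumes a full cohort of 20 and no censoring. The total effect cannot be stated, because the number of equivocal-then-confirmed progressions is unknown; the 1.3 to 4.4 points at 24 weeks is an illustration under the assumptions of Step 5. The primary ORR rule is unaffected.

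**What to change.** 1. In SAP Table 4 (footnote 1) and separately in SAP Table 3, state that when progression confirms an equivocal finding at the previous assessment, the event date is that previous assessment, per Protocol 6.7.
2. In both tables, state that this scan then does not count as an adequate progression-free assessment.
3. State whether the rule also applies to subjects assessed by RANO.
4. If the later date is intended instead, say so in SAP 3.2 as a departure from the Protocol, and apply it to all three branches of footnote 1 and to Table 3.
5. Optionally, add the date to the new-lesion text of Protocol Appendix 4. No conflict there requires it.

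The cost is a few lines of SAP text, best settled before database lock. With the Protocol rule, PFS and DOR become slightly shorter.
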